## INSTRUCTIONS:

- Use this “*TEMPLATE PROTOCOL (HRP-503)*” to prepare a study protocol outlining your research plan.
- Depending on the nature of your study, some major sections might not be applicable to your research. If so, simply mark as “N/A.” For example, a simple survey might have many sections with “N/A.” For subsections (e.g., 1.x or 8.x) you can mark as “N/A” if you are certain that the subsection is not applicable.
- Once the IRB/HRPP approves your submission, your latest approved version of the protocol will be stored in the IRB Protocol Management online system.
- If your research plan changes and you need to modify the protocol, please submit an amendment to Protocol Management with the requested modifications. Download your current protocol from Protocol Management and indicate the changes/revisions using the track changes feature in order to make review of the modifications easier to follow. If you are unable to use track changes, please create a new paragraph wherever you need to make a change, and indicate “Amendment: Date” before making a change to any section. Protocol management will store the older versions of your protocol if the IRB or HRPP staff need to compare them during the review.

## PROTOCOL TITLE:

*Include the full protocol title.*

Short Term Choline Supplementation and Cardiovascular Health in Adults

## PROTOCOL NUMBER:

*Include the number assigned in Protocol Management (verify this has been added before submitting protocol to HRPP).*

18-535

## FUNDING:

*Sponsor(s):* National Institute of Health  
*Funded already or in the proposal phase?:* Awarded and new Award in progress  
*Is Virginia Tech the primary awardee or the coordinating center of this grant or contract? If not, list the primary institution:* Click here to provide a response.

## VERSION NUMBER/DATE:

*Include the version number and date of this protocol. Versions should start at 1.0.*

1.0: 10/20/18 WIRB

2.0: 1/30/2020

3.0: 4/16/2020

4.0: 8/10/2021

## REVISION HISTORY:

*Use this table to keep track of changes. Add more rows as needed.*

Revision #	Version Date	Brief Summary of Changes (i.e., the different sections)	Consent Change?
1.0	10/20/18	Initial submission to WIRB transfer to BRANY	N
2.0	1/30/2020	Change of Study Site Location to: [name]	Y
3.0	4/16/2020	New funding source, significant changes to protocol new measurements.	Y
4.0	8/10/2021	Changes to protocol, flyer and informed consent form	Y

## 1.0 Study Summary

Study Title	Short Term Choline Supplementation and Cardiovascular Health in Adults
Study Design	2 x 4 crossover design with repeated measures and we will conduct descriptive univariate analyses on all study variables.
Primary Objective	To establish proof-of-concept for a greater reduction in glucose homeostasis following increases in gut microbiota-generated TMAO on glucose homeostasis in older compared with young adults in order to conduct a larger, more comprehensive and mechanistic trial in the future.
Secondary Objective(s)	- Obtain preliminary data for effect size generation.
Study Population	We are recruiting men and women who are between the ages of 18-79 years of age. We will recruit individuals of all races and ethnic backgrounds.
Sample Size	60 subjects
Research Intervention(s)/ Investigational Agent(s)	-Interventions (Choline and Placebo supplementation in capsule form)
Study Duration for Individual Participants	
How long will a participant spend in your study? If multiple sessions, list time required for each session plus total.
 
Visit: 1 = 1 hour
 
Visit: 2, 8, 11, 17 = 3 hours each
 
Visit: 3, 9, 12, 18 = 2 hours each
 
Visit: 4, 10, 13, 19 = 3 hours each
 
Visit: 5, 6, 7, 14, 15, 16 = 30 minutes each
 
Total Time: 36 hours

Acronyms and Definitions	
TMA = Trimethylamine
 
TMAO = Trimethylamine-N-oxide
 
T2D = Type 2 Diabetes
 
GI = Gastrointestinal
 
FMD = Flow mediated dilation
 
CGM = Continuous glucose monitor

## 2.0 Objectives

### 2.1 Describe the purpose, specific aims, or objectives of this study:

To establish proof-of-concept for a greater reduction in glucose homeostasis following increases in gut microbiota-generated TMAO on glucose homeostasis in older compared with young adults in order to conduct a larger, more comprehensive and mechanistic trial in the future.

*2.2 State the hypotheses to be tested:*

We hypothesize that gut microbiota-generated increases in plasma TMAO will be greater in older compared with young adults and this will be associated with a correspondingly greater reduction of insulin sensitivity, mixed meal tolerance, and 24-hr glycemic control in older adults.

In addition, we hypothesize that the magnitude of change in gut microbiota-generated increases in TMAO and measures of insulin sensitivity, mixed meal tolerance, and 24-hr glycemic control with the intervention will be associated with the magnitude of change in the abundance of TMA-producing bacteria and/or expression of cutC TMA lyase.

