### **3.0 Background**

*3.1 Summarize the relevant prior research on this topic and gaps in current knowledge within the field of study:*

Dysbiosis of the gut microbiota, characterized as adverse changes in the abundance and/or composition of gut microbes, has been implicated in pathophysiology of a number of chronic diseases including neurological disorders, colitis, atherosclerosis, and metabolic diseases. Several lines of evidence in both animal models and humans also implicate gut dysbiosis in the etiology of insulin resistance and T2D. Future studies are needed to understand the potential link between gut microbial composition and function with glucose homeostasis and risk of T2D. Recently, gut microbiota-generated increases in TMAO has become a novel target for the treatment of cardiovascular diseases. The results of studies in rodent models indicate a causal role of TMAO in the development of atherosclerosis and several meta-analyses support a dose-dependency of TMAO in predicting adverse CVD events. Given the close relationship between T2D and cardiovascular disease, perhaps it is not surprising that a higher prevalence of T2D has been observed in populations with elevated TMAO. The potential role of TMAO in the development of insulin resistance and T2D is supported by multiple observations. Changes in gut microbial composition with aging are observed even in the absence of overt disease. However, the role of these changes on the reduced glucose homeostasis observed with aging is unknown. Interestingly, TMAO increases with advancing age in both mice and humans. Human TMAO increases are believed to be a consequence of changes in the gut microbiota, i.e., dysbiosis. Indeed, there is an increase in the abundance of TMA-producing bacteria with aging. Importantly, and as emphasized earlier, plasma TMAO concentrations are dependent on the composition of the gut

microbiota and higher baseline TMAO concentrations are associated with larger increases in TMAO with choline loading. As such, we hypothesize that older adults will demonstrate greater gut microbiota generated increases in TMAO following choline loading compared with young adults. Furthermore, the greater gut microbiota-generated increases in TMAO following choline loading will be associated with not only a greater abundance of TMA-producing bacteria but a larger decrement in insulin sensitivity, mixed meal glucose tolerance, and a reduction in 24-hr glycemic control.

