## **4.0 Study Endpoints**

4.1 *Describe the primary and secondary **study** endpoints. See links below for discussion of study endpoints and how they may differ from study objectives. These are most common in clinical trials but are sometimes applicable to other types of biomedical research, as well as social, behavioral, or educational research. See link below for a discussion.*

[https://docs.google.com/document/d/1Wocz7K7a0hCQJPPO\\_khh511SQjhGDDGHzcOPRHR5Tw/edit?usp=sharing](https://docs.google.com/document/d/1Wocz7K7a0hCQJPPO_khh511SQjhGDDGHzcOPRHR5Tw/edit?usp=sharing)

With this study, there are three continuous measurements which will define our study endpoints. These include oral glucose tolerance, flow mediated dilation of the brachial artery and aortic pulse wave velocity measurements corresponding to arterial stiffness and a mixed meal tolerance test.

With regards to our hypothesis stated in section 2.2, our study endpoints will be as follows: Gut microbiota-generated increases in plasma TMAO will be greater in older compared with young adults and this will be associated with a correspondingly greater reduction of insulin sensitivity, mixed meal tolerance, and 24-hr glycemic control in older adults.

4.2 *Describe any primary or secondary **safety** endpoints. These should be included for all studies that are greater than minimal risk. (Minimal risk: The probability and magnitude of harm or discomfort anticipated in the research that are not greater in and of themselves than those ordinarily encountered in daily life or during the performance of routine physical or psychological examinations or tests.):*

Our safety endpoints will correspond to the potential risks that subjects may experience which are stated in section 17.1.

Potential safety endpoints which could occur with this study are as follows: 1) Any severe GI distress or complaints reported with consumption of the choline or placebo supplement, 2) Discomfort or pain which is not tolerated by the subject with blood draws, 3) Discomfort and pain due to the inflation of the BP cuff on the forearm of the participant; and 4) Discomfort which is reported when measuring arterial stiffness measurements due to slight pressure being applied to the carotid, brachial, radial and femoral arteries.

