## **8.0 Procedures Involved**

*8.1 Describe and explain the study design:*

Using a randomized cross-over design, participants will be given and asked to consume either choline or a placebo (maltodextrin) supplement for four weeks and will consume 1000 mg (500 BID) of choline or placebo per day. Testing will take place over twelve visits. Participants will complete a screening visit and two periods of three-day testing sessions before and after the four-week period of choline and placebo supplement. In between experimental sessions, there will be a two-week “washout”.

*8.2 Provide a description of:*

- *All research procedures being performed*
- *If the study has more than one procedure, session, and/or subject population, describe each procedure, session, and/or study population separately. For complex studies, you are encouraged to include a figure or chart.*

Session 1: Baseline (screening) session (Approximately 2 hours) Garvin Building, Suite 1575

Overnight Fast: Subjects will be asked to avoid eating or drinking anything except water and to avoid consuming any caffeine-containing beverages for 12 hours prior to this visit so that the test results will not be influenced by the food they eat or by the normal digestion process.

Blood Chemistry: A blood draw will be collected for choline concentrations as well glucose, cholesterol, and other factors that may impact or be reflective of vascular function/health. A needle will be inserted in an arm vein to draw blood (approximately 2 tablespoons/draw).

Urine Test: Subjects will be asked to urinate in a small cup. Sodium and other electrolytes, glucose, protein, pH, and whether there are blood cells present will be measured to determine whether it is safe for each individual to participate in the study.

Proof of COVID-19 vaccination: Subjects will be asked to bring their vaccination card against COVID-19 to the laboratory.

Medical History: Subjects will be asked to complete a medical history questionnaire, which will be used to screen for health problems (unstable heart disease) or other reasons (medications which influence study results) that would preclude participation.

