## VT 18-535 Short Term Choline Supplementation and Cardiovascular Health in Adults

**Stool Collection:** Subjects will be given a test tube and asked to collect a stool sample. Subjects will be asked to bring the sample back to the laboratory during their next scheduled visit. All supplies and instructions will be provided by the laboratory.

**Continuous Glucose Monitoring:** Glucose will be measured by a continuous glucose monitor (FreeStyle Libre Pro, Abbott). A small sensor will be placed on the subject's skin overlying the back side of their arm in order to measure glucose continuously. The sensor has a small plastic tube that is inserted into the tissue just below the skin and is held in place with sticky tape. The device will be worn for 3-4 days.

Session 3, 9, 12, 18: (Approximately 2 hours) Garvin Building, Suite 1575

**Overnight Fast:** Subjects will be asked to avoid eating or drinking anything except water and to avoid consuming any caffeine-containing beverages for 12 hours prior to this visit so that the test results will not be influenced by the food they eat or by the normal digestion process.

**Resting Blood Pressure and Heart Rate:** Blood pressure measurements will be made under quiet, comfortable ambient laboratory conditions via mercury sphygmomanometry or an automatic blood pressure monitor. Heart rate will also be determined by an automatic blood pressure cuff. Measurements will conform strictly to American Heart Association guidelines.

**Body Mass:** Body weight will be measured on a digital scale accurate to +/- 0.01 kg.

**Dietary intake analysis (24-hour recall):** Subjects will be asked to recall all the food and beverages they consumed in the previous 24-hour period.

**Blood Chemistry:** A blood draw will be collected for choline concentrations as well as glucose, cholesterol, and other factors that may impact or be reflective of vascular function/health. A needle will be inserted in an arm vein to draw blood (approximately 2 tablespoons/draw).

**Arterial Stiffness:** Carotid Ultrasonography - Common carotid artery diameters will be measured from the image obtained from an ultrasound unit (GE Vivid S6) equipped with a high-resolution linear array transducer. Applanation Tonometry - The carotid, brachial, radial and femoral artery pressure waveform and amplitude will be obtained by a fingertip probe incorporating a high-fidelity strain gauge transducer.

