## VT 18-535 Short Term Choline Supplementation and Cardiovascular Health in Adults

Endothelium Independent Vasodilation: This will be assessed by measuring brachial arterial dilation for 5 minutes following administration of 0.4 mg of sublingual nitroglycerine. Individuals will not be allowed to participate in this aspect if they take Cialis or Viagra or have a history of coronary heart disease.

24-hour Urine Collection: Subjects will be asked to collect all urine samples over a 24-hour period and bring the sample back to the laboratory during their next scheduled visit. All supplies and instructions will be provided by the laboratory.

Body Mass and Composition: Body weight will be measured on a digital scale accurate to +0.01 kg. Height will be measured with a stadiometer. Percent body fat and fat-free mass will be measured in all subjects using dual-energy x-ray absorptiometry (DEXA) (Prodigy Advance, GE Healthcare).

Pregnancy Test: If a subject is female and pre- or peri-menopausal or not postmenopausal for at least 1 year, she will be required to provide a small cup of urine for a pregnancy test.

Session 4, 10, 13, 19: (Approximately 3 hours) Garvin Building, Suite 1575

Overnight Fast: Subjects will be asked to avoid eating or drinking anything except water and to avoid consuming any caffeine-containing beverages for 12 hours prior to this visit so that the test results will not be influenced by the food they eat or by the normal digestion process.

Resting Blood Pressure and Heart Rate: Blood pressure measurements will be made under quiet, comfortable ambient laboratory conditions via mercury sphygmomanometry or an automatic blood pressure monitor. Heart rate will also be determined by an automatic blood pressure cuff. Measurements will conform strictly to American Heart Association guidelines.

Body Mass: Body weight will be measured on a digital scale accurate to +/- 0.01 kg.

Dietary intake analysis (24-hour recall): Subjects will be asked to recall all the food and beverages they consumed in the previous 24-hour period.

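### A larger plasma TMAO rise in older adults cannot be credited to the gut microbiota without information on clearance, and the 24-hour urine that could help has no stated use

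*Combined protocol and SAP*

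**What the plan says.** Section 2.2 hypothesises that "gut microbiota-generated increases in plasma TMAO will be greater in older compared with young adults". Section 4.1 carries the same statement as an endpoint, and the objective in sections 1.0 and 2.1 uses the same attribution.

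The rationale in section 3.1 names one source for higher TMAO with age: "Human TMAO increases are believed to be a consequence of changes in the gut microbiota, i.e., dysbiosis". It also says that "plasma TMAO concentrations are dependent on the composition of the gut" microbiota. Clearance, kidney function, creatinine and filtration rate are not mentioned anywhere in the protocol.

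The relevant samples in section 8.2 are:

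- **24-hour urine**, sessions 3, 9, 12 and 18: "Subjects will be asked to collect all urine samples over a 24-hour period and bring the sample back to the laboratory". No analyte or purpose is given.
- **Blood chemistry**, same sessions: "A blood draw will be collected for choline concentrations as well as glucose, cholesterol, and other factors". Neither TMAO nor a kidney-function measure is named.
- **Screening urine**, session 1, for safety: "Sodium and other electrolytes, glucose, protein, pH, and whether there are blood cells present will be measured".
- **Stool**, sessions 2, 8, 11 and 17. The second hypothesis in section 2.2 relates changes in TMAO and glucose measures to change in TMA-producing bacteria and/or cutC expression. Section 3.1 also expects the larger rise to go with greater bacterial abundance.

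The section 5.2 model estimates choline against placebo. It has no age term, clearance covariate or urine variable.

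**The concern.** A plasma concentration reflects both how fast a substance appears and how fast it is removed. The hypothesis reads an age difference in plasma rise as a difference in appearance from the gut. If the age groups also differ in clearance, the predicted result could arise with no microbiota difference.

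The crossover protects the choline-placebo comparison within a person. It does not protect a comparison between age groups, because age is not randomised and each person's difference is still divided by that person's own clearance.

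One argument in section 3.1 fits either explanation. It notes that people with higher baseline TMAO have larger rises on choline, but lower clearance alone would scale up both.

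At stake is the wording of the main mechanistic conclusion. Section 3.3 looks ahead to interventions aimed at the gut microbiota, and section 1.0 says the pilot is meant to lead to a larger mechanistic trial.

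**Working it through.** The plan gives no figure on this point to reproduce. Its stated effect size (section 14.1: 20/32 = 0.625, given as 0.63) concerns insulin sensitivity and is not an input here.

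**Inputs.** The hypothesis and samples are from sections 2.2, 4.1 and 8.2. Total N = 60 is from section 14.1. Assumed, because the documents are silent: clearance lower in older adults by a fraction f of 0.10 to 0.40, identical production in both groups, and a 30/30 age split.

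**Step 1: absolute rise.** With appearance rate R and clearance CL, the steady-state level is C = R/CL. The rise on choline is ΔC = ΔR/CL. Subtracting placebo or baseline leaves CL in the denominator. With equal ΔR, the older/young ratio of rises is 1/(1 − f).

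| Clearance lower by | Older/young ratio | Excess rise |
|---|---|---|
| 10% | 1/0.90 = 1.11 | 11% |
| 20% | 1/0.80 = 1.25 | 25% |
| 30% | 1/0.70 = 1.43 | 43% |
| 40% | 1/0.60 = 1.67 | 67% |

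**Step 2: ratio scale.** (R1/CL)/(R0/CL) = R1/R0, so a stable clearance cancels. The plan does not say whether an increase is a difference or a ratio. Section 5.2 allows a transformation for major non-normality but names none, so the scale is open.

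**Step 3: urinary excretion.** Over 24 hours, excretion = R × (fraction excreted in urine). Clearance does not enter, provided collections are complete, the steady state holds and the urinary fraction is similar in both age groups.

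**Step 4: chance of a significant age difference with identical production.** Simulation of 30 against 30, log-normal rise, two-sided 5% t-test on the log of the absolute rise, 20,000 runs per setting. The between-person CV is assumed.

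| Clearance lower by | CV 40% | CV 60% | CV 100% |
|---|---|---|---|
| 10% | 18% | 11% | 7% |
| 20% | 60% | 34% | 17% |
| 30% | 94% | 69% | 37% |
| 40% | >99% | 93% | 66% |

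On urinary excretion the same test stays at about 5% throughout, which follows from the step 3 assumptions.

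**Step 5: timing of the urine.** Section 8.2 hands out one week of capsules at session 4 and at each of sessions 5, 6 and 7, which makes four weeks. Section 8.1 places the later test sessions after the four-week period, and the later urine collection starts at session 9 (session 18 in the second period). The shared description of sessions 4, 10, 13 and 19 also hands out a week of capsules. Read literally, that includes session 10, just before washout, and session 19, the last visit. The text therefore does not settle whether supplements are being taken during that collection, so a steady state on choline is not established.

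**The case against.** The strongest reply has several parts.

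- **No direction is documented.** Mass balance shows only that clearance matters. A reader might infer that older participants clear TMAO more slowly, so that the predicted result is expected to be an artefact. The documents do not say this. The point stands as something the design cannot exclude.
- **Silence is not non-use.** A reader might infer that the urine will go unanalysed. The protocol only fails to state a use. Its analyte lists are open-ended and do not name plasma TMAO either, although that is the hypothesis variable. This part of the reply stands.
- **The written analysis makes no age comparison.** A reader might infer that following section 5.2 produces the false claim. It does not, because the model has no age term. That gap comes first and needs its own correction.
- **The stool data help.** Baseline stool allows bacterial abundance to be compared between age groups, and section 3.1 predicts an association. This is a partial safeguard. Abundance and cutC expression measure neither production nor clearance, and section 5.2 gives no model for them.
- **Urinary TMAO is not gut production.** It reflects total appearance, including host absorption and conversion of TMA. This stands and limits what the fix can show.
- **This is a pilot about glucose.** A link between plasma TMAO and glucose measures does not depend on why TMAO is high, and no hypothesis is labelled primary. That lowers the stakes. But the objective and endpoint statement both make the gut attribution, so it should be supported or reworded.

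**Conclusion.** The concern holds as a limit on attribution. As written, the plan cannot tell greater TMAO production in older adults from slower clearance, and so cannot support calling an age difference in plasma rise gut-generated.

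The possible size is an 11% to 67% larger absolute rise for clearance 10% to 40% lower, with production equal. Both the range and its direction are assumptions. The figures do not apply to a post/pre ratio when clearance is stable, and the significance probabilities also depend on the assumed split and CV.

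The documents do not show that a clearance difference exists in this population or that the trial will reach a false conclusion. The trial can run as designed. The endpoint definition, the analysis and the wording of the conclusion should change.

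**What to change.** 1. **Sections 4.1 and 8.2:** name TMAO as an analyte in plasma and in the 24-hour urine already collected at sessions 3, 9, 12 and 18. Measure urinary creatinine to check completeness. Define the rise and its scale.
2. **Section 5.2:** add an age-by-treatment term. Report the older-versus-young contrast for plasma rise on both absolute and ratio scales, and for urinary TMAO excretion.
3. **Sensitivity analysis only:** add creatinine to the blood already drawn and repeat the plasma contrast adjusted for estimated filtration rate. This should not be the main analysis, because estimated filtration rate is closely tied to age.
4. **Conclusion rule, fixed in advance:** describe greater TMAO production in older adults only if urinary excretion agrees. Describe it as gut-generated only if the stool abundance or cutC data also support it. Otherwise report higher plasma TMAO.
5. **Sections 8.1 and 8.2:** reconcile the passages on whether the post-supplement urine is collected while supplements are still being taken.

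The cost is a small assay charge, with no added visit, procedure or participant. The check depends on complete collections and on a similar urinary excreted fraction in both age groups. A lower fraction in older adults would understate their production, making the check conservative against a false claim; a higher fraction would do the reverse.
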